11. TRIAL DESIGN

11.1 General considerations

PARABLE is a proof of concept, randomised, double-blind, double-dummy, phase II, parallel group, controlled trial. It will enrol 250 patients with cardiovascular risk factors, elevated NP and LAVI above 28 mL/m².

Standard dosing regimen: Following selection, discontinuation of existing angiotensin converting enzyme (ACE) inhibitor and a washout period of 36 hours, or angiotensin receptor blocker (ARB) (no washout necessary), PARABLE will randomly assign subjects to LCZ696 100mg twice daily titrated to LCZ696 200mg twice daily or valsartan 80mg twice daily titrated to valsartan 160 mg twice daily for 18 months (see Figure 1a).

Lower dosing regimen: A starting dose of LCZ696 50 mg twice daily or valsartan 40mg twice daily will be used for subjects not currently taking an ACE inhibitor or an ARB, and for subjects previously taking low doses of these agents (as per Investigator judgement). A lower dosing regimen should also be used for subjects with a systolic BP of ≥ 100 mm to 110mmHg at screening or baseline. The dose of LCZ696 and valsartan will be doubled every 2 to four weeks to the target dose of 200mg and 160mg twice daily for LCZ696 and valsartan respectively, as tolerated by the subject. (See Figure 1b)

(LCZ696 200mg twice daily delivers similar exposure of valsartan (assessed by AUC) as Diovan 160mg twice daily. This dose delivers approximately 90% of its maximal neprilysin inhibition (Novartis Company Information)).

[figure not shown]

Figure 1a. Study design for subjects titrated with the standard starting dose of study drug

[figure not shown]

Figure 1b. Study design for subjects titrated with the lower starting dose of study drug

11.2 Selection of study population

Eligible patients will be male or female, over 40 years old, with cardiovascular risk factors, elevated NP and LAVI above 28 mL/m².

11.2.1 Inclusion criteria

To be eligible for inclusion, each patient must meet each of the following criteria at screening (Visit 1) and must continue to fulfil these criteria at baseline (Visit 2).

1. Age > 40yrs with cardiovascular risk factor(s) including at least one of:
 - a. History of hypertension (medicated for greater than one month);
 - b. History of diabetes;
2. Elevated NP: Elevated NP: BNP between 20 and 280pg/ml or NT-proBNP values between 100 pg/ml and 1,000 pg/ml within 6 months prior to screening or at screening
3. LAVI > 28 mL/m² obtained during Doppler Echocardiography within 6 months prior to screening or at screening
4. Subjects must give written informed consent to participate in the study and before any study related assessments are performed.

11.2.2 Exclusion criteria

1. A history of heart failure.
2. Asymptomatic left ventricular systolic dysfunction defined as LVEF <50% on most recent measurement.
3. Systolic blood pressure <100mmHg
4. Persistent atrial fibrillation.
5. History of hypersensitivity, allergy or intolerance to LCZ696, ARB or neprilysin therapy or to any of the excipients or other contraindication to their use.
6. Previous history of intolerance to recommended target doses for ARBs
7. Subjects who require treatment with both an ACE inhibitor and an ARB
8. Presence of haemodynamically significant mitral and /or aortic valve disease.
9. Presence of hemodynamically significant obstructive lesions of left ventricular outflow tract, including aortic stenosis.
10. Conditions that are expected to compromise survival over the study period.
11. Serum potassium level > 5.2 mmol/L at screening.
12. Severe renal insufficiency (eGFR <30 mL per minute per 1.73 m²).
13. Hepatic dysfunction (AST or ALT values exceeding 3x ULN)
14. Concomitant use of aliskiren
15. History of angioedema.
16. History or evidence of drug or alcohol abuse within the last 12 months
17. Malignancy or presence of any other disease with a life expectancy of < 2 years
18. Women who are pregnant, breast-feeding, or women of child bearing potential not using estro-progestative oral or intra-uterine contraception or implants, or women using estro-progestative oral or intra-uterine contraception or implants but who consider stopping it during the planned duration of the study. A postmenopausal state is defined as no menses for 12 months without an alternative medical cause. (Contraception must be continued for one week following discontinuation of study drug).
19. Concomitant participation in other intervention trials
20. Participation in any investigational drug trial within one month of visit 1.
21. Refusal to provide informed consent
22. Subjects with contraindications to MRI
 - a) Brain aneurysm clip
 - b) Implanted neural stimulator
 - c) Implanted cardiac pacemaker or defibrillator
 - d) Cochlear implant
 - e) Ocular foreign body (e.g. metal shavings)
 - f) Other implanted medical devices: (e.g. Swan-Ganz catheter)
 - g) Insulin pump
 - h) Metal shrapnel or bullet.
23. Any surgical or medical condition which might significantly alter the absorption, distribution, metabolism, or excretion of study drugs, including but not limited to any of the following:
 - a) History of major gastrointestinal tract surgery including gastrectomy, gastroenterostomy, or bowel resection.
 - b) Inflammatory bowel disease during the 12 months prior to Visit 1.

- c) Any history of pancreatic injury, pancreatitis or evidence of impaired pancreatic function/injury as indicated by abnormal lipase or amylase.
- d) Evidence of hepatic disease as determined by any one of the following: SGOT or SGPT values exceeding 3 x ULN at Visit 1, a history of hepatic encephalopathy, a history of oesophageal varices, or a history of portocaval shunt.

No additional exclusions may be applied by the Investigator in order to ensure that the study population will be representative of all eligible patients.

12. STUDY ASSESSMENTS AND PROCEDURES

Informed consent will be obtained prior to any study-related procedures being undertaken.

12.1 Screening visit (Visit 1)

Prior to Visit 1, the Investigator shall perform a 'pre-screening' exercise and review the STOP-HF database to identify subjects that may potentially meet the inclusion/exclusion criteria (e.g. age, risk factors for heart failure and other co-morbidities).

The Investigator shall contact those subjects that meet the inclusion and exclusion criteria based on the information available in the STOP-HF database and provide information to them about the clinical trial and ascertain their interest in participating in the trial. (Prior to any contact, www.rip.ie should be checked to identify deceased patients). This contact must be documented in the patients' medical notes. Patients may also contact the STOP-HF clinic directly in response to an advertisement. Patients may also be referred from other clinics, hospital departments or healthcare professionals.

If the subject expresses interest in participating in the trial, they will be invited to attend a screening visit (Visit 1). They will be given a Subject Information Leaflet and Informed Consent Form. They will be given sufficient time to consider their participation in the study and to ask any questions concerning the study (See section 22.5 for further information on the informed consent process). Informed consent must be received before any study related procedures are carried out. Only a qualified medical doctor may obtain informed consent.

Following informed consent, various clinical laboratory assessments will be carried out to assess/confirm eligibility (e.g. potassium, liver function, eGFR). The Investigator should review the subject's medical history to confirm that no other exclusion criteria related to the study or contraindications to study medication are known. For NP, any elevated value (BNP >20pg/ml or NT-proBNP >100 pg/ml) obtained in the previous 6 months is acceptable. For LAVI, any elevated value (> 28 mL/m²) obtained in the previous six months is acceptable.

An appointment for Visit 2 is scheduled for up to two weeks later.

Following Visit 1 and following a review of laboratory assessment to confirm eligibility, patient randomisation will take place. The patient will be assigned to one of the two treatment arms in accordance with the randomisation scheme.

Table 1. Study interventions

Treatment arm	# of subjects randomised	Type	Compound	Min dose	Max dose (target dose)	Frequency	Route
Arm 1	~125	Active	LCZ696	50 mg*	200 mg	Twice daily	Oral
Arm 2	~125	Comparator	Valsartan	40 mg*	160 mg	Twice daily	Oral

12.2 Baseline visit (Visit 2)

Eligible patients will undergo a 36-hour washout period if they were previously taking an ACE inhibitor[†] and be randomized to one of two arms for 18 months:

[1] Intervention arm: LCZ696 100mg twice daily, titrated after two weeks to 200mg twice daily on top of usual medical care or

[2] Control arm: ARB (valsartan) 80mg twice daily, titrated after two weeks to 160 twice daily on top of usual medical care.

[†]LCZ696 must not be initiated until 36 hours after taking the last dose of ACE inhibitor.

*A starting dose of LCZ696 50mg twice daily or valsartan 40mg twice daily will be used for subjects not currently taking an ACE inhibitor or an ARB, and/or for subjects previously taking low doses of these agents (as per Investigator judgement). A lower dosing regimen should also be used for subjects with a systolic BP of ≥ 100 mm to 110mmHg at screening or baseline. The dose of LCZ696 and valsartan will be doubled every 2 to four weeks to the target dose of 200mg and 160mg twice daily for LCZ696 and valsartan respectively, as tolerated by the subject.

All subjects will be reviewed two weeks after dose titration for tolerability issues (e.g. symptomatic hypotension, hyperkalaemia, renal dysfunction). In cases of poor tolerability, temporary down-titration of study drug, co-medication or discontinuation will be considered (see Appendix 10).

Additional medications or interventions will be administered at the discretion of the attending physician. The use of an ACE inhibitor an ARB concomitantly with the study drug after randomisation is strictly prohibited.

The Investigator shall complete a 'Wallet Card' for each patient. Patients will be advised to carry the card with them at all times and to present the card to medical personnel should they require any medical care outside the study while participating in the study.

12.3 Follow up visits (Visits 3-11)

Table 2 outlines the schedule of clinical assessments, blood sampling, imaging and follow-up that will apply in PARABLE. Follow-up visits will take place in the STOP-HF Service, St Michael's Hospital, Dun Laoghaire.

A follow-up visit will also take place two weeks after each dose titration (i.e. at week two and four and six).

If any subject refuses to return for these assessments or is unable to do so, every effort should be made to contact him/her by telephone and these attempts should be recorded in the subject's paper case report form (pCRF). If one visit is postponed or brought forward, it should not result in the next visit being postponed or brought forward. The next visit, if at all possible, should adhere to the original time schedule.

Table 2. Study assessments and procedures

Visit number	1	2	3	4	5	6	7	8	9	10	11	12
Assessment	Wk-2 Screening	D0 Baseline	Wk 2	Wk 4	Wk 6	Wk 13 / Mth 3	Wk 26 / Mth 6	Wk 39 / / Mth 9	Wk 52 / Mth 12	Wk 65 / Mth 15	Wk 78 / Mth 18 (EOS)	Mth 27 (Optional sub-study)
			± 3d	± 3d	± 3d	± 7d	± 7d	± 7d	± 7d	± 7d	± 7d	± 28
Assessment of eligibility	X											X
Pregnancy test (WOCBP)	X	X	X	X	X	X	X	X	X	X	X	X
Informed consent	X											X
Randomisation		X										
Medical history	X											
Physical exam	X	X	X	X	X	X	X	X	X	X	X	X
Height (H) and weight (W)		H/W						W			W	H/W
Waist/hip circumference		X						X			X	X
Vital signs (BP and pulse)	X	X	X	X	X	X	X	X	X	X	X	X
Natriuretic peptide	X [#]	X	X	X	X	X	X	X	X	X	X	X
Biomarkers		X			X	X	X	X	X	X	X	X
U&E, LFT, Alk phos	X (no alk phos)	X	X	X	X	X	X	X	X	X	X	X
Haematology	X	X						X			X	X
eGFR	X	X						X			X	X
HbA1c, lipid profile, iron studies		X						X			X	X
cGMP (urinary)		X			X	X		X			X	X
ABPM		X						X			X	X
Electrocardiography (ECG)		X						X			X	X
Doppler echocardiography	X [*]	X [†]						X			X	X
Cardiac MRI [‡]		X									X	
Questionnaires ^{**}		X						X			X	X
Concomitant medications	X	X	X	X	X	X	X	X	X	X	X	
Adverse events			X	X	X	X	X	X	X	X	X	X
Dispense medication		X	X	X	X	X	X	X	X	X		
Drug accountability			X	X	X	X	X	X	X	X	X	
Holter monitor (optional)											X	

*Source: results of these assessments may be filed in the Subject Study File on the original source document (questionnaires) or a copy of the source document (e.g. laboratory report, Echo report, ECG (this must be a copy of the original), ABPM printout etc.)

‡ Echo may be needed at Visit 1 if one hasn't been performed in the previous six months.

† If an Echo is performed at screening, it does not have to be repeated at baseline, unless the investigator decides otherwise. Baseline echo must be performed within 90 days prior to baseline.

** The SMMSE and MoCA cognitive assessment questionnaire will also be administered five years after the patient's end of study visit.

Z If the patient had an MRI in the previous six weeks, then there is no need for a repeat MRI at baseline

NP levels may be needed at Visit 1 if one hasn't been performed in the previous six months.

12.4 Assessments

12.4.1 Laboratory parameters

Peripheral venous blood samples will be drawn at the timelines shown in Table 2. Laboratory examinations are analysed in St Michael's Hospital laboratory or St Vincent's Hospital laboratory. Methods for sampling and handling are detailed in the PARABLE laboratory manual (HBT-GCP-SOP-16 'Handling Laboratory Samples for the PARABLE Study'). Evaluations will include the following:

- Biochemistry
 - Urea & Electrolytes (U&E)
 - Liver Function Tests (LFT)
 - Alkaline Phosphatase
 - Lipid profile
 - HbA1c
 - Iron studies
- Haematology
 - Full blood count

Sample processing and analysis will be done as per local standard operating procedures. The local hospital laboratory should provide the report to the Investigator who is responsible for the clinical assessment of the results. Any abnormality should be assessed for its clinical significance. Any clinically significant value should be recorded as an AE in the CRF and followed up.

12.4.2 eGFR assessments

The eGFR to determine eligibility of the subject for screening into the trial will be calculated at Visit 1 (screening) from the serum creatinine concentration. The eGFR will be further measured at Visit 8 (month 9) and Visit 11 (EOS).

eGFR will only be calculated using the following formula: $eGFR \text{ (mL/min/1.73 m}^2\text{)} = 175 \times (\text{standardized SCr in mg/dL})^{-1.154} \times (\text{age in years})^{-0.203} \times (0.742 \text{ if female}) \times (1.212 \text{ if black})$, where SCr is the standardized serum creatinine value.

12.4.3 Urinary biomarkers

A spot office urine sample (random sample) will be collected from subjects at Visit 2 (baseline), Visit 5 (week 6), Visit 6 (month 3), Visit 8 (month 9) and Visit 11 (EOS/18 month) for assessment of cGMP and atrial natriuretic peptide (ANP).

12.4.4 Biomarkers

Peripheral blood samples and plasma for biomarker analysis will be drawn at the timelines shown in Table 2. Samples will undergo immediate serum separation by centrifuge at 1500 rcf (relative centrifugal force) for 15 minutes at 21°C. The serum and plasma will then be separated into aliquots and stored at -80°C. They will be

transported on dry ice to the Conway Institute, University College Dublin for simultaneous analysis of selected biomarkers from the Table below using validated analytical techniques:

- | | |
|--------------|-------------------|
| • Col1A1 | • Aldosterone |
| • PICP | • Creatinine |
| • PIIINP | • IL-6 |
| • MMP-2 | • IL-1R1 |
| • MMP-3 | • IL-R2 |
| • MMP-9 | • IL-2RA |
| • TIMP-1 | • IL-6RA |
| • TIMP-4 | • IL-17RA |
| • GP6 | • TNF-alpha R1/R2 |
| • sST-2 | • ANP |
| • hsTroponin | • MCP1 |
| • Galectin-3 | • CT1 |
| • PRA | • GDF15 |
| • uPAR | • TR-AP |
| • CD163 | • E/P-Selectins |
| • uPA | • vWF |
| • | • Cystatin B |
| • PON3 | • TF-P1 |

12.4.5 Serum BNP and NT-proBNP

NP measurements required for eligibility will be based on levels measured within the last 6 months or at screening.

Serum BNP from the peripheral circulation will be measured using the Alere Triage[®] BNP test, a POC fluorescence immunoassay. Several drops of EDTA anticoagulated whole blood or plasma is added to the sample port of the test device which is then inserted in to the meter. The concentration of BNP in the specimen is directly proportional to the fluorescence detected. The results are displayed on the meter screen approximately 15 minutes from the addition of the specimen.

Serum NT-proBNP from the peripheral circulation will be measured by the St Vincent's Healthcare Group Laboratory according to standard hospital policy.

12.4.6 Medical history

The subject's medical history will be recorded at the screening visit.

12.4.7 Demographics

The subject's date of birth, gender and race will be recorded at the screening visit.

12.4.8 Physical exam

A short physical exam will include the examination of general appearance and a cardiac exam at every visit. Information will be recorded in the CRF. Significant findings that are present prior to the start of study drug must be included in the relevant section of the subject's CRF. Significant findings made after the start of study drug which meet the definition of an AE must be recorded on an AE form in the subject's CRF.

12.4.9 Vital signs

Vital signs will be assessed at every visit. This will include BP and pulse measurements. BP will be measured by using a standard sphygmomanometer with an appropriate size cuff and the non-dominant arm in the sitting position after 5 minutes of rest. This BP (and not 24h ABPM) will be used to confirm eligibility and inform dosing decisions.

12.4.10 Height, weight and waist/hip circumference

Height in centimetres (cm) will be measured at Visit 2 (baseline). Body weight (to the nearest 0.1 kilogram [kg] in indoor clothing without shoes) and waist/hip circumference (at natural waistline, which is located above the belly button and below the rib cage; start at one hip and wrap the tape measure around the rear, making sure the tape is over the largest part of the buttocks) (to the nearest centimetre [cm] in indoor clothing) will be measured at Visit 2 (baseline), Visit 8 (month 9) and Visit 11 (EOS).

12.4.11 Ambulatory blood pressure monitoring (ABPM)

ABPM will be measured at Visit 2 (baseline), Visit 8 (month 9) and Visit 11 (EOS).

The device employed for ABPM analysis will be the SpaceLab 90207 oscillometric device. Depending on arm circumference, two standard cuff sizes will be used with application to the non-dominant arm. Subjects will be instructed to go about their usual activities with minimal restrictions. The systolic blood pressure (BP), diastolic BP, and heart rate of each subject will be automatically measured every 30 minutes for 24 consecutive hours with a properly calibrated SpaceLab 90207 device. The device will be fitted and removed by a cardiovascular technician/nurse blinded to study treatment allocation. If quality criteria are not met, one repeat measurement will be allowed during the following 1–2 month period. Nocturnal dipping is defined as subjects with a more than 10% fall in nocturnal BP relative to daytime values. Non-dipping is defined as a less than 10% nocturnal fall in BP.

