10.2 Endpoints

Primary endpoint:

Change in left atrial volume index (LAVI) measured by cMRI over 18 months.

Secondary endpoints:

1. Left ventricular function using Doppler Echocardiography (average E/e') between baseline and 18 months
2. Left atrial volume index (Doppler Echocardiography LAV)/BSA* between baseline and 9 months
3. Left atrial function measured as total cMRI LAEF ((LAVimax-LAVimin)/LAVimax) over 18 months
4. Left atrial function measured as cMRI left atrial stroke volume index (LAVmax-LAVmin)/BSA*, or LAVimax-LAVimin over 18 months
5. Left ventricular structure (cMRI LVMi indexed to BSA*) over 18 months
6. Left ventricular function (cMRI LVEF) over 18 months
7. Measures of vascular compliance (ABPM pulse pressure) between baseline and 18 months
8. Change in log transformed NT-proBNP between baseline and 18 months
9. Time to first all cardiovascular death and major adverse cardiac events (MACE) requiring hospitalisation over 18 months. MACE includes arrhythmia (including atrial fibrillation/flutter), transient ischaemic attack, stroke, valvular heart disease, myocardial infarction, peripheral or pulmonary thrombosis/embolus or heart failure
10. Primary endpoint analysed per protocol.

*BSA calculated using the DuBois formula

Exploratory endpoints:

11. Left atrial function measured as cMRI left atrial cardiac index ((LAVimax-LAVimin) x heart rate) between baseline and 18 months

12. Left atrial function as cMRI myocardial strain measured using feature tracking
13. Left ventricular structure (as cMRI LVESV, LVEDV, Fractal Analysis), all indexed to BSA* between baseline and 18 months
14. Left ventricular function, measured as cMRI left ventricular stroke volume index (LVESVi-LVEDVi) between baseline and 18 months
15. Left ventricular function, measured as cMRI left ventricular cardiac index ((LVESVi-LVEDVi) x heart rate) between baseline and 18 months
16. Left ventricular function as cMRI myocardial strain using feature tracking between baseline and 18 months
17. Left ventricular function as cMRI e'
18. Evaluation of treatment effects on cMRI measures of right atrial and structure and function (RAVI, RAEF, RVEF, SV, CI, E', E/e')
19. Left atrial function using Doppler Echocardiography (E/A ratio)
20. Left ventricular structure using Doppler Echocardiography (LVMI, LVESVI, LVEDVI)
21. Left ventricular function using Doppler Echocardiography (LVEF, stroke volume (SV), cardiac index (CI), Lateral or medial e' and lateral or medial E/e')

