22. Change in log transformed BNP, NTproBNP/BNP ratio and other related peptides, e.g. ANP, urinary cGMP between baseline and 9 months and baseline and 18 months
23. Change in the following parameters of 24-hour ABPM between baseline and 9 months and baseline and 18 months: Systolic blood pressure, diastolic blood pressure and heart rate
24. Change in resting (clinic measured) systolic blood pressure, diastolic blood pressure and heart rate between baseline and 9 months and baseline and 18 months
25. Incidence of all cardiovascular death and MACE requiring hospitalisation over 18 months
26. Incidence of all cardiovascular related serious adverse events (SAEs) over 18 months
27. Incidence of all-cause death and SAEs requiring hospitalisation over 18 months

28. Incidence of all SAEs over 18 months
29. Incidence of all-cause adverse events (AEs) by system organ class over 18 months
30. Time to first event analysis using Kaplan Meier survival curves for cardiovascular death or MACE requiring hospitalisation, cardiovascular-related SAEs, death or all-cause emergency hospitalisations, all-cause SAE
31. Impact of LCZ696 on endpoints in a subset of patients with or without baseline atrial cardiomyopathy, using EHRA/HRS/APHRS/SOLAECE 2016 consensus definition; a complex of electrophysiological (e.g. atrial fibrillation, atrial flutter), structural/architectural (e.g. LAVI >34ml/m²) or contractile (e.g. LAEF, elevated E/A ratio) on cMRI or Doppler Echocardiography, at 9 and 18 months
32. Impact of LCZ696 on prevalent and new onset atrial cardiomyopathy using EHRA/HRS/APHRS/SOLAECE 2016 consensus definition (defined as a complex of electrophysiological (e.g. atrial fibrillation, atrial flutter), structural/architectural (e.g. LAVI >34ml/m²) or contractile (e.g. LAEF, elevated E/A ratio) on cMRI or Doppler Echocardiography) at 9 and 18 months
33. Impact of LCZ696 on primary and secondary endpoints, at 9 and 18 months dependent on BNP above or below 50pg/mL, median BNP, NTproBNP and NTproBNP/BNP ratio at baseline
34. Correlation between Doppler Echocardiography and cMRI measures of the following at baseline and 18 months:
 - Left atrial structure and function (LAVi, LAEF)
 - Left ventricular structure and function (e.g. LVMi, LVSVi, LVCi, LVEF, e')
 - Correlation of cMRI-e' with left atrial and left ventricular feature tracking analysis

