13.4 Dispensing the study drug

All study drug is provided to the investigator site labelled. Medication labels are in English and comply with the legal requirements for clinical trials in Ireland.

At each visit, study subjects will be provided with two medication 'kits'; one containing the study drug (LCZ696 or valsartan) and one containing placebo drug corresponding to their assigned treatment arms and dose level, sufficient to last until the next scheduled visit. Records of each dispensing shall be maintained using a drug accountability log (HBT-GCP-FM-22; 'Study Drug Inventory and Subject Assignment Log').

Table 2 and 3 below summarises the study drug that will be dispensed at the various clinic visits for subject on the standard dosing schedule and the lower dosing schedule respectively. (A lower starting dose of LCZ696 50mg twice daily or valsartan 40mg twice daily will be used for subjects not currently taking an ACE inhibitor or ARB, for subjects previously taking low doses of these agents (as per Investigator judgement) and for subjects with a systolic BP of ≥ 100 mm to 110mmHg at screening or baseline).

The procedure for the dispensing/allocation of medication pack is described in HBT-GCP-SOP-17 'Study Drug Management for the PARABLE Study'.

Subjects will be required to take the study drug and matching placebo twice a day (morning and evening) for the duration of the study. Patients will be instructed to take their morning dose at approximately 08.00 and their evening dose at approximately 19.00. The medications should be taken with a glass of water with or without food. If the subject misses a dose, he/she should take it as soon as possible, unless if it is almost time for the following scheduled dose. In this case, the subject should skip the missed dose and return back to his/her regular study drug administration schedule. The patient should be instructed to contact the Investigator if he/she is unable to take the study drug as proscribed for any reason.

Table 2. Study drug dispensed (standard dosing schedule)

Visit #	Dose level	LCZ696	Valsartan
1 (screening)	-	-	-
2 (Day 0 /baseline)	2	
 • LCZ696 100mg tablets • Placebo to match Valsartan 80mg tablets 	
 • Valsartan 80mg tablets • Placebo to match LCZ696 100mg tablets

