14. SAFETY REPORTING

The safety and tolerability of the study drugs will be evaluated starting from the administration of the study drug (Visit 2) through to EOS visit. Information regarding all AEs will be collected at each study visit based on information provided spontaneously by the subject and/or through questioning of the subject.

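### The ambulatory blood pressure repeat rule allows a baseline recorded on study drug and a month-18 value recorded after treatment; if such repeats are analysed, secondary endpoint 7 is biased towards no difference

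*Combined protocol and SAP*

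**What the plan says.** Section 12.4.11 schedules ambulatory blood pressure monitoring (ABPM) at Visit 2 (baseline), Visit 8 (month 9) and Visit 11 (month 18, end of study). The repeat rule makes no distinction between these visits: "If quality criteria are not met, one repeat measurement will be allowed during the following 1–2 month period". The section does not define the quality criteria, and it does not say whether a repeat replaces the failed value.

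Two items in section 10.2 use these recordings. Secondary endpoint 7 is "Measures of vascular compliance (ABPM pulse pressure) between baseline and 18 months". Exploratory endpoint 23 begins "Change in the following parameters of 24-hour ABPM between baseline and 9 months and baseline and 18 months" and covers systolic pressure, diastolic pressure and heart rate.

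The schedule (Table 2 in section 12.3) places baseline ABPM, randomisation and first dispensing at Visit 2. Section 14 evaluates safety "starting from the administration of the study drug (Visit 2) through to EOS visit", which confirms that dosing begins at that visit. Section 12.2 has the standard LCZ696 schedule "titrated after two weeks to 200mg twice daily on top of usual medical care". On the lower schedule, Table 3 in section 13.4 reaches the top dose level at day 28.

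The synopsis and section 11.1 give 18 months of treatment. The section 12.3 schedule marks dispensing at Visits 2 to 10 only, and section 13.4 describes kits "corresponding to their assigned treatment arms and dose level, sufficient to last until the next scheduled visit".

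**The concern.** The repeat window runs only forward from the failed recording. That does little harm at Visit 8, where the patient is mid-treatment and a repeat is merely late. At the two ends it changes what is measured. A repeat after Visit 2 follows the first dose, so it is not an untreated baseline. A repeat after Visit 11 falls outside the 18-month treatment period, so it is not a month-18 value on treatment.

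Other baseline measurements in the protocol look backward. The baseline echocardiogram must fall in the 90 days before the baseline visit, and an MRI from the preceding six weeks may serve as baseline. Visit 11 itself has a window of ±7 days, which a repeat one to two months later exceeds.

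At stake is a named secondary endpoint. If the arms differ in pulse pressure, patients with a repeated baseline have part of that difference subtracted from their change, and patients with a repeated month-18 recording have part of it missing.

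**Working it through.** **Inputs from the documents.** ABPM visits and the repeat rule (12.4.11); first dose at Visit 2 (12.3 schedule, section 14); titration (12.2, and Table 3 in 13.4); 18-month treatment (synopsis, 11.1); two-sample t-test for continuous variables, with further models adjusted for baseline (16.1). The plan gives no ABPM effect, standard deviation, power or failure rate, so there is no figure of its own to reproduce.

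**Timing.** A post-Visit 2 repeat is after the first dose however soon it is done. By one to two months the standard schedule is at its top level; on the lower schedule this is so from day 28 at the earliest. For Visit 11, exploratory objective 9 concerns persistence nine months after drug discontinuation, and the follow-up visit is at month 27. Since 27 − 9 = 18, drug ends at month 18, and a later repeat falls after the treatment period.

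**Size.** Assume that repeats are used as the analysed values and that repeat shares are the same in both arms. Let

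- D = true between-arm difference in change at month 18;
- fb, fe = shares of patients with a repeated baseline and a repeated month-18 recording;
- r = share of D already present at the baseline repeat;
- l = share of D lost at the month-18 repeat.

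The expected between-arm difference is D × fb × r in the baseline value and D × (1 − fe × l) in the month-18 value. The expected difference in change is therefore D × (1 − fb × r − fe × l).

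All shares below are assumptions, with fb = fe:

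| Repeats at each end | r = l = 0.5 | r = l = 1 |
|---|---|---|
| 2% | 1 − 0.01 − 0.01 = 0.98 | 1 − 0.02 − 0.02 = 0.96 |
| 5% | 1 − 0.025 − 0.025 = 0.95 | 1 − 0.05 − 0.05 = 0.90 |
| 10% | 1 − 0.05 − 0.05 = 0.90 | 1 − 0.10 − 0.10 = 0.80 |

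A simulation at 10% per end with r = l = 1 gave 0.80.

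For the baseline to month-9 changes in endpoint 23, only the baseline term applies, because a Visit 8 repeat is still within treatment. The factor is 1 − fb × r, for example 0.90 at 10% with r = 1.

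**Baseline-adjusted models.** With slope b on baseline, the factor is 1 − b × fb × r − fe × l. For an assumed b = 0.5, 10% repeats and r = l = 1, it is 1 − 0.05 − 0.10 = 0.85, against 0.80 for the change score.

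**Scale in power terms (illustration only).** A two-sided 5% comparison that would have 80% power without repeats has power of about Φ(2.80 × k − 1.96) when the effect is multiplied by k. That is about 76% at k = 0.95, 71% at k = 0.90 and 61% at k = 0.80.

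**The case against.** The strongest counter-case is that the size is unknown and may be small. No failure rate is given; at 2% per end the loss is only 2–4%. The time course is not documented either. Both arms deliver valsartan, so what counts is how fast the difference between arms appears and fades. The endpoint is framed as vascular compliance, the rationale cites collagen turnover of 80 to 120 days, and persistence off drug is itself an exploratory question. The affected items are one secondary and one exploratory endpoint. Under the assumptions above the bias is conservative, and the primary cMRI endpoint is untouched. All of this stands. It limits the size but does not make a Visit 2 or Visit 11 repeat valid.

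Three stronger readings are tempting but not supported.

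- A reader might infer that every baseline repeat is at target dose, or that every month-18 repeat is one to two months off drug. The wording sets a period during which a repeat may occur, so it may come sooner. On the lower schedule, doubling every two to four weeks means that two doublings can take up to eight weeks.
- A reader might infer that adjusting for a contaminated baseline removes still more of the effect. With a slope below 1 it removes less than the change score does.
- A reader might take contamination as established. The protocol allows a repeat but does not state that it becomes the analysed value.

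The drug-supply tables in section 13.4 have rows running to Visit 11, whereas the section 12.3 schedule marks no dispensing there. These must be reconciled. The stated 18-month duration still places a Visit 11 repeat outside the treatment period.

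**Conclusion.** The concern holds in conditional form. Followed as written, the rule can yield an on-drug baseline and a month-18 value from after the treatment period, and no section prevents either from being analysed. The bias is towards no difference if three conditions are met: repeats are used as the analysed values; a between-arm effect exists that is partly present early or partly lost off drug; and repeat shares are similar in the two arms. If the drugs do not differ, there is nothing to shrink.

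The expected difference is multiplied by 0.98–0.96 at 2% repeats per end, 0.95–0.90 at 5% and 0.90–0.80 at 10%, for r and l between 0.5 and 1. Baseline adjustment reduces the baseline part of the loss without removing it and leaves the month-18 part. The timing conflict is certain from the documents; the size is not. The point should be fixed because the remedy is cheap and can be settled before unblinding.

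**What to change.** **Protocol, section 12.4.11.** Limit the one-to-two-month repeat to Visit 8. Accept a Visit 2 recording or repeat as baseline only if completed before the first dose, and a Visit 11 recording or repeat as month 18 only if completed within the 18-month treatment period. Where visits are still to come, fit the device early enough to leave room for a repeat. This may be too late here: section 25.1 planned the last treatment-period visit for December 2020, before Version 10.0 was approved in February 2021.

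**Analysis, before unblinding.** Compare each ABPM date with the first and last dose dates. For endpoints 7 and 23, treat repeats outside the limits above as missing. Handle them by multiple imputation and not by carrying month 9 forward; section 16.1 names both methods, so the choice must be stated. Include these repeats only in a sensitivity analysis, and report their number by arm and visit. Apply this exclusion to repeats only. Drug is dispensed at the same visit as the baseline ABPM, so a first 24-hour recording may overlap the opening doses, and excluding those as well could cost far more data.

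**Consistency.** Reconcile the Visit 11 dispensing rows in section 13.4 with the section 12.3 schedule.

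**Cost.** An amended rule, a date check and, if few recordings were repeated, a few values that become missing.
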